### 1.3.3 Schedule of Activities: Part 2 (Panel E/G Titration Regimen 1)

Part 2 Panel E/G Titration Regimen 1 MK-8189/matching placebo 16 mg x 3 days and 24 mg x 7 days																			
	Screening	Washout			Intervention										Poststudy	Notes			
Scheduled Day		-6	-2	-1	1	2	3	4	5	6	7	8	9	10	11	12	~17		
Administrative Procedures																			
Informed Consent	X																Section 8.1.1		
Informed Consent for Future Biomedical Research	X																Section 8.1.1.2		
Inclusion/Exclusion Criteria	X			X													Only specific criteria will be reviewed prior to randomization.		
Participant Identification Card	X																Section 8.1.3		
Medical History (includes psychiatric history and substance usage)	X																Substances: drugs, alcohol, and caffeine Section 8.1.4		
Prior/Concomitant Medication Review	X-----X														X		Section 8.1.5		
Washout from Antipsychotics (Panel E only)		X	X														Discontinue medication at least 5 days or at least 3 half-lives (whichever is longer) prior to Day -1. Section 8.1.5.1		

Part 2 Panel E/G Titration Regimen 1 MK-8189/matching placebo 16 mg x 3 days and 24 mg x 7 days																		
	Screening	Washout			Intervention												Poststudy	Notes
Scheduled Day		-6	-2	-1	1	2	3	4	5	6	7	8	9	10	11	12	~17	
Assignment of Allocation Number (Randomization)					X													Section 8.1.7
MK-8189/Placebo Administration					X	X	X	X	X	X	X	X	X	X				Sections 8.1.8 and 6.3.1
Standard Meals a				X	X	X	X	X	X	X	X	X	X	X	X			Section 5.3.1
Domiciling in Clinic b		X-----X																Section 8.1.11
Follow-up Phone Call																X		
Safety Procedures																		
Full physical examination	X			X											X		X	Section 8.3.1
Height	X																	Section 8.3.1
Weight	X				X										X		X	Section 8.3.1
Full Neurological Exam	X				X													Section 8.3.7 and Appendix 11
Targeted Neurological Exam						X			X			X			X		X	Section 8.3.7 and Appendix 11
Vital Signs (heart rate, blood pressure) c	X			X	X			X				X		X		X		Section 8.3.2 and Section 8.3.2.1
Orthostatic Vital Signs (heart rate, blood pressure) d	X			X	X			X				X		X		X		Section 8.3.2.2
Vital Signs (respiratory rate, body temperature) e	X				X			X				X		X		X		Section 8.3.2 and Section 8.3.2.1
12-lead ECG f	X				X			X				X		X		X		Section 8.3.3

Part 2 Panel E/G Titration Regimen 1 MK-8189/matching placebo 16 mg x 3 days and 24 mg x 7 days																		
	Screening	Washout		Intervention													Poststudy	Notes
Scheduled Day		-6	-2	-1	1	2	3	4	5	6	7	8	9	10	11	12	~17	
Serum $\beta$ -hCG (WOCBP only)	X																	
Urine Pregnancy Test (WOCBP only)				X														
Serum FSH (WONCBP only)	X																	Appendix 2
HIV, Hepatitis B and C Screen (per site SOP)	X																	Appendix 2
UDS/BDS (per site SOP) g	X			X														Appendix 2
Laboratory Safety Test (hematology, chemistry, urinalysis) e	X			X	X		X					X		X		X		Appendix 2
Columbia Suicide Severity Rating Scale (C-SSRS)- Baseline Version	X																	Section 4.2.3
Columbia Suicide Severity Rating Scale (C-SSRS)- Since Last Assessment Version e				X	X		X		X		X		X		X			Section 4.2.3
Barnes Akathisia Rating Scale (BARS) e, h				X	X		X		X		X		X		X			Section 4.2.1.1
Abnormal Involuntary Movement Scale (AIMS) e, h				X	X		X		X		X		X		X			Section 4.2.1.1
Simpson Angus Scale (SAS) e, h				X	X		X		X		X		X		X			Section 4.2.1.1
Bond and Lader Visual Analog Scale (VAS) e				X	X		X		X		X		X		X			Section 4.2.1.1
Brief Psychiatric Rating Scale (BPRS) (Panel E only) e	X			X	X		X		X		X		X		X			Section 4.2.1.1

Part 2 Panel E/G Titration Regimen 1 MK-8189/matching placebo 16 mg x 3 days and 24 mg x 7 days																			
	Screening	Washout		Intervention														Poststudy	Notes
Scheduled Day		-6	-2	-1	1	2	3	4	5	6	7	8	9	10	11	12	~17		
AE/SAE review	X	-----X														Section 8.4			
Pharmacokinetics																			
Blood for Plasma MK-8189 and/or Metabolites Assay i					X				X						X	X	X	Section 8.6.1	
Biomarkers																			
Blood for Genetic Analysis j					X													Collect predose from enrolled participants only. Section 8.8	

AE=adverse event; BDS=blood draw screen; FSH=follicle stimulating hormone; SAE=serious adverse event; SOP=standard operating procedure; UDS=urine drug screen; WOCBP=women of childbearing potential; WONCBP=women of nonchildbearing potential

a. Meals should be given at approximately the same time every day starting on Day -1 through Day 11. Day -1 will be time-matched to Day 1. Breakfast will be given at ~1-hour postdose, lunch given at ~4 hours postdose, a snack given at ~8 hours postdose and dinner at ~12 hours postdose. All meals will follow the completion of all specified procedures at that timepoint.

b. Participants will be confined minimally from Day -6 until Day 12 procedures are complete.

c. Single HR and BP measurements will be obtained at all timepoints unless otherwise noted. On the following days, specific timepoints are noted:

- Day -1 (triplicate measurements): Time-matched to 8, 16 and 24 hours postdose vital signs.
- Day 1, Day 4 and Day 10: 8, 16 and 24 hours postdose
- Day 12: Time-matched to 24-hour postdose vital signs

d. Orthostatic assessments in HR and BP will follow semi-recumbent vital sign assessments. Participants should be standing for approximately 2 minutes prior to the orthostatic assessments. Orthostatic HR and BP measurements will be obtained on:

- Day -1: Time-matched to 8, 16 and 24 hours postdose orthostatic vital signs.
- Day 1, Day 4 and Day 10: 8, 16 and 24 hours postdose
- Day 12: Time-matched to the 24-hour postdose orthostatic vital signs

e. Scheduled assessments are completed predose on dosing days and at any time on non-dosing days.

f. Single 12-lead safety ECG measurements will be taken at all postdose timepoints. On the following days, specific timepoints are noted:

- Day 1: Triplicate measurements within 2 hours prior to dosing
- Day 1, Day 4 and Day 10: 8, 16 and 24 hours post-dose

g. Screening UDS is mandatory; any additional UDS are conducted per site SOP. UDS prior to randomization will be done on the day of admission.

Part 2 Panel E/G Titration Regimen 1 MK-8189/matching placebo 16 mg x 3 days and 24 mg x 7 days																		
Scheduled Day	Screening	Washout		Intervention										Poststudy	Notes			
		-6	-2	-1	1	2	3	4	5	6	7	8	9	10	11	12	~17	
h. Additional BARS, AIMS and SAS assessments will be conducted as soon as possible when there are observed or reported complaints of dystonia and/or akathisia (See Section 8.3.6).																		
i. MK-8189 plasma PK sample collection:																		

• Day 1 and Day 4: predose, 2, 6, 8, 10, 12, 16 and 24 hours postdose.

• Day 10: predose, 2, 6, 8, 10, 12, 16, 24, 36 and 48 hours postdose

• Optional sample when signs of dystonia and/or akathisia occur.

• Leftover main study plasma will be stored for future biomedical research if the participant consents to future biomedical research.

																		
j. This sample will be drawn for CYP2C9 and for planned analysis of the association between genetic variants in DNA and drug response. If the IRB/IEC does not approve of the planned analysis of the association between DNA variation and drug response, or if there is a local law or regulation prohibiting the same, data analysis will be limited to CYP2C9. Leftover extracted DNA will be stored for future biomedical research.																		

### 1.3.4 Schedule of Activities: Part 2 (Panel E/G Titration Regimen 2)

Part 2 Panel E/G Titration Regimen 2 MK-8189/matching placebo 24 mg x 7 days																
	Screening	Washout		Intervention										Poststudy	Notes	
Scheduled Day		-6	-2	-1	1	2	3	4	5	6	7	8	9	~14		
Administrative Procedures																
Informed Consent	X														Section 8.1.1	
Informed Consent for Future Biomedical Research	X														Section 8.1.12	
Inclusion/Exclusion Criteria	X			X											Only specific criteria will be reviewed prior to randomization. Section 5	
Participant Identification Card	X														Section 8.1.3	
Medical History (includes psychiatric history and substance usage)	X														Substances: drugs, alcohol, and caffeine Section 8.1.4	
Prior/Concomitant Medication Review		X-----X													Section 8.1.5	
Washout from Antipsychotics (Panel E only)		X	X												Discontinue medication at least 5 days or at least 3 half-lives (whichever is longer) prior to Day- 1. Section 8.1.5.1	

Part 2 Panel E/G Titration Regimen 2 MK-8189/matching placebo 24 mg x 7 days															
	Screening	Washout	Intervention											Poststudy	Notes
Scheduled Day		-6 -2	-1	1	2	3	4	5	6	7	8	9	~14		
Assignment of Allocation Number (Randomization)				X											Section 8.1.7
MK-8189/Placebo Administration				X	X	X	X	X	X	X					Sections 8.1.8 and 6.3.1
Standard Meals a			X	X	X	X	X	X	X	X	X				Section 5.3.1
Domiciling in Clinic b		X-----													Section 8.1.11
Follow-up Phone Call													X		
Safety Procedures															
Full physical examination	X		X									X		X	Section 8.3.1
Height	X														Section 8.3.1
Weight	X			X								X		X	Section 8.3.1
Full Neurological Exam	X		X												Section 8.3.7 and Appendix 11
Targeted Neurological Exam					X			X				X		X	Section 8.3.7 and Appendix 11
Vital Signs (heart rate, blood pressure) c	X		X	X			X			X		X		X	Section 8.3.2 and Section 8.3.2.1
Orthostatic Vital Signs (heart rate, blood pressure) d	X		X	X			X			X		X		X	Section 8.3.2.2
Vital Signs (respiratory rate, body temperature) e	X			X			X					X		X	Section 8.3.2 and Section 8.3.2.1
12-lead ECG f	X			X			X					X		X	Section 8.3.3
Serum β-hCG (WOCBP only)	X														
Urine Pregnancy Test (WOCBP only)			X												

Part 2 Panel E/G Titration Regimen 2 MK-8189/matching placebo 24 mg x 7 days															
	Screening	Washout	Intervention										Poststudy	Notes	
Scheduled Day		-6 -2	-1	1	2	3	4	5	6	7	8	9	~14		
Serum FSH (WONCBP only)	X														Appendix 2
HIV, Hepatitis B and C Screen (per site SOP)	X														Appendix 2
UDS/BDS (per site SOP) g	X		X												Appendix 2
Laboratory Safety Test (hematology, chemistry, urinalysis) e	X		X		X					X		X		X	Appendix 2
Columbia Suicide Severity Rating Scale (C-SSRS)- Baseline Version	X														Section 4.2.3
Columbia Suicide Severity Rating Scale (C-SSRS)- Since Last Assessment Version e			X		X		X				X		X		Section 4.2.3
Barnes Akathisia Rating Scale (BARS) e, h			X		X		X			X		X		X	Section 4.2.1.1
Abnormal Involuntary Movement Scale (AIMS) e, h			X		X		X			X		X		X	Section 4.2.1.1
Simpson Angus Scale (SAS) e, h			X		X		X			X		X		X	Section 4.2.1.1
Bond and Lader Visual Analog Scale (VAS) e			X		X		X			X		X		X	Section 4.2.1.1

Part 2 Panel E/G Titration Regimen 2 MK-8189/matching placebo 24 mg x 7 days																	
	Screening	Washout	Intervention										Poststudy	Notes			
Scheduled Day			-6	-2	-1	1	2	3	4	5	6	7	8	9	~14		
Brief Psychiatric Rating Scale (BPRS) (Panel E only) e	X				X		X			X				X		X	Section 4.2.1.1
AE/SAE review		X												X			Section 8.4
Pharmacokinetics																	
Blood for Plasma MK-8189 and/or Metabolites Assay i					X	X	X				X	X	X				Section 8.6.1
Biomarkers																	
Blood for Genetic Analysis j					X												Collect predose from enrolled participants only. Section 8.8

AE=adverse event; BDS=blood draw screen; ECG=electrocardiogram; FSH=follicle stimulating hormone; SAE=serious adverse event; SOP=standard operating procedure; UDS=urine drug screen; WOCBP=women of childbearing potential; WONCBP=women of nonchildbearing potential

a. Meals should be given at approximately the same time every day starting on Day -1 through Day 8. Day -1 will be time-matched to Day 1. Breakfast will be given at ~1-hour postdose, lunch given at ~4 hours postdose, a snack given at ~8 hours postdose and dinner at ~12 hours postdose. All meals will follow the completion of all specified procedures at that timepoint.

b. Participants will be confined minimally from Day -1 until Day 9 procedures are complete.

c. Single HR and BP measurements will be obtained at all timepoints unless otherwise noted. On the following days, specific timepoints are noted:

- Day -1 (triplicate measurements): Time-matched to 8, 16 and 24 hours postdose vital signs.
- Day 1, Day 4 and Day 7: 8, 16 and 24 hours postdose
- Day 9: Time-matched to 24-hour postdose vital signs

d. Orthostatic assessments in HR and BP will follow semi-recumbent vital sign assessments. Participants should be standing for approximately 2 minutes prior to the orthostatic assessments. Orthostatic HR and BP measurements will be obtained on:

- Day -1: Time-matched to 8, 16 and 24 hours postdose orthostatic vital signs.
- Day 1, Day 4 and Day 7: 8, 16 and 24 hours postdose
- Day 9: Time-matched to 24-hour postdose orthostatic vital signs

e. Scheduled assessments are completed predose on dosing days and at any time on non-dosing days.

f. Single 12-lead safety ECG measurements will be taken at all postdose timepoints. On the following days, specific timepoints are noted:

- Day 1: Triplicate measurements within 2 hours prior to dosing
- Day 1 and Day 4: 8, 16 and 24 hours post-dose

Part 2 Panel E/G Titration Regimen 2 MK-8189/matching placebo 24 mg x 7 days														
Scheduled Day	Screening	Washout	Intervention										Poststudy	Notes
	-6	-2	-1	1	2	3	4	5	6	7	8	9	~14	
g.	Screening UDS is mandatory; any additional UDS are conducted per site SOP. UDS prior to randomization will be done on the day of admission.													
h.	Additional BARS, AIMS and SAS assessments will be conducted as soon as possible when there are observed or reported complaints of dystonia and/or akathisia (See Section 8.3.6).													
i.	MK-8189 plasma PK sample collection:													
	
 
Day 1: predose, 2, 6, 8, 10, 12 and 16 hours postdose
 
Day 2 and Day 3: predose, 2, 6 and 8 hours postdose
 
Day 7: predose, 2, 6, 8, 10, 12, 16, 24, 36 and 48 hours postdose
 
Optional sample when signs of dystonia and/or akathisia occur.
 
Leftover main study plasma will be stored for future biomedical research if the participant consents to future biomedical research.
 
													
j.	This sample will be drawn for CYP2C9 and for planned analysis of the association between genetic variants in DNA and drug response. If the IRB/IEC does not approve of the planned analysis of the association between DNA variation and drug response, or if there is a local law or regulation prohibiting the same, data analysis will be limited to CYP2C9. Leftover extracted DNA will be stored for future biomedical research.													

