Laboratory Safety Test (hematology, chemistry, urinalysis) e	X			X						X		X		X	Appendix 2
Columbia Suicide Severity Rating Scale (C-SSRS)-Baseline Version	X														Section 4.2.3
Columbia Suicide Severity Rating Scale (C-SSRS)-Since Last Assessment Version e				X		X			X			X		X	Section 4.2.3
Barnes Akathisia Rating Scale (BARS) e, i				X		X			X			X		X	Section 4.2.1.1

	Screening	Washout	Part 1 (Panel A and Panel B or C)											Poststudy	Notes
			-1	1	2	3	4	5	6	7	8	9	~14		
Scheduled Day		-6 -2													
Abnormal Involuntary Movement Scale (AIMS) e, i			X		X			X				X		X	Section 4.2.1.1
Simpson Angus Scale (SAS) e, i			X		X			X				X		X	Section 4.2.1.1
Bond and Lader Visual Analog Scale (VAS) e			X		X			X				X		X	Section 4.2.1.1
Brief Psychiatric Rating Scale (BPRS) e	X		X		X			X				X		X	Section 4.2.1.1
AE/SAE review	X													X	Section 8.4
Pharmacokinetics															
Blood for Plasma MK-8189 and/or Metabolites Assay j				X	X	X	X			X	X	X			Section 8.6.1
Biomarkers															
Blood for Genetic Analysis k					X										Collect predose from enrolled participants only. Section 8.8

AE=adverse event; BDS=blood draw screen; FSH=follicle stimulating hormone; SAE=serious adverse event; SOP=standard operating procedure; UDS=urine drug screen; WOCBP=women of childbearing potential; WONCBP=women of nonchildbearing potential

a. Meals should be given at approximately the same time every day starting on Day -1 through Day 8. Day -1 will be time-matched to Day 1. Breakfast will be given at ~ 1-hour postdose, lunch given at ~ 4-hours postdose, a snack given at ~ 8-hours postdose and dinner at ~ 12-hours postdose. All meals will follow the completion of all specified procedures at that timepoint.

b. Participants will be confined minimally from Day -6 until Day 9 procedures are complete.

c. Single HR and BP measurements will be obtained at all timepoints unless otherwise noted. On the following days, specific timepoints are noted:

- Panel A and Panel B:
  - Day -1 (triplicate measurements): Time-matched to 8, 16 and 24 hours postdose vital signs.
  - Day 1, Day 4 and Day 7: 8, 16 and 24 hours postdose
  - Day 9: Time-matched to 24-hour postdose vital signs
- Panel C
  - Day -1 (triplicate measurements): Time-matched to 8, 16 and 24 hours postdose vital signs.
  - Day 1, Day 2, Day 3 and Day 7: 8, 16 and 24 hours postdose

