If tolerability issues are due to elimination of dose titration, it will likely be evident within the first few days of dosing MK-8189. Thus, an initial assessment of tolerability will be made following 3 days of dosing in approximately 8 participants. If MK-8189 is generally well tolerated based on AEs, an additional 8 participants will be enrolled into Panel B receiving Titration Regimen 2. If Titration Regimen 2 is not generally well tolerated in Panel B (either after assessment of the initial cohort [n=8] or full cohort [n=16]), an additional 8 participants

will be enrolled in Panel A such that a total of 16 participants will receive Titration Regimen 1.

Panel C will enroll 16 participants with schizophrenia disorder and receive Titration Regimen 3. Participants will be randomized to active or placebo. Participants randomized to MK-8189 will receive 8 mg on Day 1 (2 x 4-mg tablets), 16 mg on Day 2 (1 x 12-mg tablet and 1 x 4-mg tablet) and 24 mg (2 x 12-mg tablets) on Days 3 to 7. Participants randomized to placebo will receive the same number of tablets matching the MK-8189 tablet strength in the active group.

All participants will be confined to the unit from at least Day -6 until Day 9 assessments are complete.

## Part 2

The goal of Part 2 is to evaluate MK-8189 safety, tolerability and PK and titration regimens in elderly participants with schizophrenia disorder (Panels D and E) and healthy elderly participants (Panel F and G). Participants will be randomized to MK-8189 or placebo. Participants with schizophrenia will be washed off their current antipsychotic therapy. The washout may start with a down titration of the antipsychotic treatment during the screening phase per direction of the investigator. Participants should not receive antipsychotics for at least 5 days or 3 half-lives (whichever is longer) prior to Day -1. For longer half-life antipsychotics (e.g. aripiprazole and brexpiprazole), if deemed appropriate by the investigator, a participant may stop treatment (i.e. cessation of AAP) as an outpatient, but should be confined the clinical research unit within a week of stopping treatment and minimally beginning on Day -6. Healthy elderly participants (Panel F and G) will be domiciled by Day -1.

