Assuming that dosing was generally well tolerated in Panel D, the selection of the titration regimen for Panel E will be dependent on the safety and tolerability data observed in Part 1 and will be made jointly between the investigator(s) and the Sponsor and documented in a protocol clarification letter. Note: as shown in the Protocol Summary (Section 1), if Titration Regimen 1 or 3 is selected for evaluation, dosing at 24 mg will be extended to ensure evaluation of this MK-8189 dose for 7 days in the elderly population.

An initial cohort (n=4) will be dosed with the selected titration regimen from Part 1 to initially assess tolerability in a small number of participants. Tolerability will be assessed after the third dose and will determine the dose regimen scheme for the remainder of the participants; if well tolerated, the remainder of the cohort will be enrolled in the selected dose regimen (n=12). However, if the selected regimen is not well tolerated, an additional cohort of 4 participants will be enrolled in an alternate (more conservative) dose regimen as shown in [\[Figure 2\]](#). Depending on the initial dose regimen selected for evaluation, this process may be repeated as outlined in [\[Figure 2\]](#) such that up to 3 Titration Regimens may be evaluated with the objective to have 1 of the titration regimens evaluated in ~ 16 participants. The decision to initiate an alternate titration regimen will be documented in a protocol clarification letter.

Figure 2 Part 2 Panel E/G Alternate Dose Regimens if Starting Regimen is Titration Regimen 1 or Titration Regimen 2

Participants will be confined to the unit from at least Day -6 until the 48-hour postdose assessments are complete (Day 12, Day 9 and Day 11 for Titration Regimen 1, Titration Regimen 2 and Titration Regimen 3, respectively).

For Part 1 and Part 2, all dose titration decisions (where applicable) will be made jointly by the investigator and the Sponsor. However, if appropriate medical care necessitates a down-titration, the investigator may do so independent of consultation with the Sponsor. Any changes to the protocol-specified titration schedule (eg, the participant remains at their current dose or is down titrated) will be documented in a protocol clarification letter.

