### **8.1.5 Prior and Concomitant Medications Review**

#### **8.1.5.1 Prior Medications**

The investigator or qualified designee will review prior medication use, including any protocol-specified washout requirement, and record prior medication taken by the participant within 3 months before starting the study. Use of any prescription or nonprescription medication during the washout period should first be discussed between the investigator and Sponsor, unless appropriate medical care necessitates that therapy or vaccination should begin before the investigator and Sponsor can consult. Note: medications permitted under Section 6.5 of the protocol do not need to be discussed prior to use.

All participants will be washed out from their antipsychotic medication at least 5 days or at least 3 half-lives (whichever is longer) prior to Day -1. The washout may start with a down titration of the antipsychotic treatment during the screening phase per direction of the investigator. For longer half-life antipsychotics (e.g. aripiprazole and brexpiprazole), if deemed appropriate by the investigator, a participant may stop treatment (i.e. cessation of AAP) as an outpatient, but should be confined to the clinical research unit within a week of stopping treatment and minimally beginning on Day -6.

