### **8.1.11 Domiciling**

Healthy elderly participants will be domiciled by Day -1. Participants with schizophrenia will report to the CRU at least 6 days prior to treatment with MK-8189 on Day 1 and all participants will remain in the unit until the 48-hours postdose procedures are complete. At the discretion of the investigator, participants may be requested to remain in the CRU longer.

Participants may be permitted to leave the unit, for emergency situations only, during the domiciling period at the discretion of the investigator after discussion with the Sponsor. The decision how to monitor the participant will be at the discretion of the investigator after discussion with the Sponsor.

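### The Regimen 2 schedule for Panels E and G lets Panel E be admitted on Day -1, five days later than the Day -6 minimum in Sections 4.1 and 8.1.11

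*Combined protocol and SAP*

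**What the plan says.** The Section 1.3.4 schedule covers Panel E and Panel G under Titration Regimen 2 (24 mg for seven days). Footnote b, attached to the "Domiciling in Clinic" row, does not separate the panels: "Participants will be confined minimally from Day -1 until Day 9 procedures are complete". The antipsychotic washout row of the same schedule is restricted to Panel E.

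Section 4.1, describing Panel E, says: "Participants will be confined to the unit from at least Day -6 until the 48-hour postdose assessments are complete". It then lists the end day for each regimen and gives Day 9 for Regimen 2. Section 8.1.11 says: "Participants with schizophrenia will report to the CRU at least 6 days prior to treatment with MK-8189 on Day 1". Both sections have healthy elderly participants in the unit by Day -1.

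Part 1 includes the same seven-day 24 mg regimen (Panel B) with the same Day 9 end. Footnote b of its schedule reads "Participants will be confined minimally from Day -6 until Day 9 procedures are complete", and Section 4.1 for Part 1 agrees: "All participants will be confined to the unit from at least Day -6 until Day 9 assessments are complete".

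**The concern.** For Panel E under Regimen 2, the protocol gives two minimum admission days. A Panel E participant admitted on Day -1 would satisfy footnote b and breach Sections 4.1 and 8.1.11.

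The days at issue are those on which participants aged 61 to 80 with schizophrenia are off their antipsychotics before dosing. Section 6.5.1 anticipates withdrawal symptoms in this period and allows a benzodiazepine and zolpidem to treat them. Section 8 makes adherence to the schedule of activities a requirement of study conduct, so a schedule footnote is not something a site may disregard. What is at stake is inpatient supervision during washout. The statistical analysis is untouched.

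**Working it through.** No plan figure needs to be recomputed. The check sets the confinement rules side by side and counts days.

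| Place | Who | Latest start | End |
|---|---|---|---|
| 1.3.1, footnote b | Part 1 (schizophrenia) | Day -6 | Day 9 |
| 1.3.2, footnote b | Panels D and F | Day -6 | Day 15 |
| 1.3.3, footnote b | Panels E and G, Regimen 1 | Day -6 | Day 12 |
| **1.3.4, footnote b** | **Panels E and G, Regimen 2** | **Day -1** | **Day 9** |
| 1.3.5, footnote b | Panels E and G, Regimen 3 | Day -6 | Day 11 |
| 4.1, Part 2 | Panel E, all regimens | Day -6 | Day 9 for Regimen 2 |
| 8.1.11 | Schizophrenia | 6 days before Day 1 | 48 hours postdose |
| 4.1 and 8.1.11 | Healthy elderly | Day -1 | 48 hours postdose (8.1.11) |

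1. **Same day in both sections.** The schedules go from Day -1 to Day 1 with no Day 0. Six days before Day 1 is therefore Day -6, so Sections 8.1.11 and 4.1 agree for Panel E.
2. **End day.** The last Regimen 2 dose is on Day 7, and 48 hours later is Day 9. All the texts agree here; only the start differs.
3. **Gap for Panel E.** Days -6, -5, -4, -3 and -2 are required by Sections 4.1 and 8.1.11 but not by footnote b, which is five days. Antipsychotics must be stopped at least 5 days (or 3 half-lives, if longer) before Day -1. Five days before Day -1 is Day -6, so the gap is the whole of the shortest permitted washout.
4. **Gap for Panel G.** None, since Day -1 is the healthy-elderly rule.
5. **Is there an exemption?** No text exempts Panel E under Regimen 2 from the Day -6 rule. Section 8.1.5.1 allows longer half-life antipsychotics to be stopped as an outpatient, but even then the participant "should be confined to the clinical research unit within a week of stopping treatment and minimally beginning on Day -6". That sentence covers only those drugs, so it supports Day -6 without being the general rule.
6. **How many participants.** Section 4.1 starts Panel E with 4 participants and adds 12 if the regimen is tolerated. If Regimen 2 is used and not tolerated, the footnote covers 4. If it is continued, it covers 4 + 12 = 16. If it is never used in Panel E, it covers none.

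A smaller mismatch runs the other way. Footnote b in Sections 1.3.2, 1.3.3 and 1.3.5 applies Day -6 without excepting healthy Panels F and G, who need only be in by Day -1.

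**The case against.** The strongest reply is that the texts can all be obeyed at once. Footnote b sets a minimum, and Day -1 is the correct common minimum for a table shared with Panel G, so admitting Panel E on Day -6 satisfies every statement. The row carrying the footnote also points to Section 8.1.11, which states the split by population. Section 8 binds sites to the study design requirements as a whole and does not rank a schedule footnote above Section 4.1. Some unconfined washout is already part of the design, because down-titration may begin during screening. Finally, the problem arises only if Regimen 2 is chosen for Panel E.

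Most of this stands, and it limits the risk to a site working from the footnote alone. The Domiciling row also appears to begin in the washout columns, but the table as reproduced is too broken to give that much weight. The reply does not remove the conflict. A minimum matters for what it permits, and this one permits a Day -1 admission that two other sections forbid. The outpatient washout that the design allows still ends in confinement by Day -6.

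**Conclusion.** The concern holds. Footnote b of Section 1.3.4 is wrong as written for Panel E and right for Panel G. This is an internal inconsistency; the intended design is clear from Sections 4.1 and 8.1.11 and is not in dispute.

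The error is five days in one of five schedules, covering 0, 4 or about 16 participants depending on whether Regimen 2 is used and continued in Panel E. Those counts assume the cohort sizes in Section 4.1, with no replacements and no repeat of the panel. They are the participants the footnote governs, not a forecast of late admissions. The point should be corrected because it concerns supervision of elderly patients during antipsychotic washout, but it does not threaten the trial. For healthy Panels F and G, the opposite mismatch risks only unneeded confinement or a nominal deviation.

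**What to change.** Replace footnote b in Section 1.3.4 with a rule for each panel, for example: *Panel E: inpatient from Day -6 or earlier. Panel G: inpatient by Day -1. Both panels: stay through completion of the Day 9 procedures.* Simply changing Day -1 to Day -6 would be wrong, because it would bind the healthy participants in Panel G.

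As a minor consistency edit, make the same split in footnote b of Sections 1.3.2 (Panel D against Panel F, end Day 15), 1.3.3 (Panel E against Panel G, end Day 12) and 1.3.5 (Panel E against Panel G, end Day 11).

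The cost is the wording of one footnote and three optional edits, by protocol clarification letter or in the next amendment. Procedures, sample size and analysis do not change.
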